6. ASSESSMENT AND FOLLOW-UP

6.1. Neurodevelopmental evaluation

All babies will have detailed neurodevelopmental evaluation including Bayley Scales of Infant Development (BSID-III or IV if available), Gross Motor Function Classification System (GMFCS), and hearing and vision assessment between 18 to 24 months of age. Severe disability will be defined as any one of the following: both cognitive and language composite BSID-III scores <70, GMFCS level 3–5, hearing impairment requiring hearing aids, or blindness. Moderate disability will be defined as both cognitive and language composite BSID-III scores between 70 and 84 and one or more of the following: GMFCS level 2, hearing impairment with no need for amplification or a persistent seizure disorder. The outcomes will also be assessed by categorisation of these scores and by including mortality as an outcome. An adverse outcome will be defined as death or, in survivors, moderate or severe disability.

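### Section 6.1 leaves survivors with one composite below 70 and the other 70–84 outside both disability categories, so a worse child can count as not adverse while a milder one counts as adverse

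*Protocol*

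**What the plan says.** Protocol section 6.1 (Neurodevelopmental evaluation) defines the outcome at 18 to 24 months in three steps.

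- **Severe.** "Severe disability will be defined as any one of the following: both cognitive and language composite BSID-III scores <70". The other items, each sufficient alone, are GMFCS level 3 to 5, a need for hearing aids, and blindness.
- **Moderate.** "Moderate disability will be defined as both cognitive and language composite BSID-III scores between 70 and 84 and one or more of the following". So the scores alone are not enough: the child must also have at least one of three accompanying signs, which are motor function at GMFCS 2, a hearing loss that needs no amplification, and persisting seizures.
- **Adverse outcome.** "An adverse outcome will be defined as death or, in survivors, moderate or severe disability".

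The section adds that outcomes will also be assessed by categorising the scores and by including mortality. It has no rule for a child whose two composites fall in different bands.

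**The concern.** Disability categories should be ordered: if one child is at least as impaired as another in every domain and worse in one, that child should not receive the better classification. Here the severe score criterion needs both composites below 70, while the moderate criterion has a floor of 70 for both. A child with one composite under that floor and the other above it fails both tests. The lower score removes the child from the moderate category without moving the child into the severe one.

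Death or moderate or severe disability is the only composite clinical outcome the protocol defines, and all babies are to be assessed for it. If impaired survivors are counted as unaffected, the adverse-outcome rate is too low, and any use made of that outcome inherits the error.

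**Working it through.** The protocol states no figure for this point, so there is none to reproduce. The check is logical, followed by an illustration of scale.

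**1. Two children under the rules as written**

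| | Cognitive | Language | GMFCS | Severe? | Moderate? | Adverse? |
|---|---|---|---|---|---|---|
| Child A | 75 | 75 | 2 | No | Yes | Yes |
| Child B | 65 | 75 | 2 | No: language is not below 70 | No: cognitive is not in 70–84 | No |

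B equals A on language and motor function and is worse on cognition. B stays not adverse even if hearing loss without amplification and a persistent seizure disorder are added.

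**2. All score bands, for a child with GMFCS 2 and no severe item other than the scores**

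| Cognitive \\ Language | 85 or more | 70–84 | Below 70 |
|---|---|---|---|
| 85 or more | not adverse | not adverse | not adverse |
| 70–84 | not adverse | moderate | **not adverse** |
| Below 70 | not adverse | **not adverse** | severe |

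The two bold cells are the hole: each is worse than the moderate cell but classed as better.

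**3. Full enumeration**

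Profiles: cognitive band (3) × language band (3) × GMFCS 0–1, 2, 3–5 (3) × hearing none, unaided loss, aids (3) × blindness (2) × seizure disorder (2) = 324.

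- As written, 38 pairs are inverted: one profile is at least as bad in every domain and worse in at least one, yet not adverse, while the milder profile is adverse.
- They involve 14 distinct worse profiles: 2 (which composite is the lower) × 7 (non-empty combinations of the three signs) = 14.
- All 14 are classed as not adverse, so the error runs in one direction only.
- With the moderate score criterion changed to both composites below 85 and not severe, exactly these 14 become moderate, no other profile changes, and no inversion remains.

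These are counts of possible profiles, not of children.

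**4. Scale, under assumptions**

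The protocol gives no composite means, SDs or correlation. Assumed: bivariate normal scores, mean 85, 90 or 95, SD 15 or 18, correlation 0.7 or 0.8, the same mean and SD for both composites.

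- P(one composite below 70, the other 70–84) = 2 × P(cognitive below 70, language 70–84). Over the grid this runs from 0.040 (mean 95, SD 15, correlation 0.8) to 0.129 (mean 85, SD 18, correlation 0.7).
- Survivors: section 1.1 quotes 28% mortality in cooled babies with moderate or severe HIE. 220 × (1 − 0.28) = 158.
- Children with mixed scores: 0.040 × 158 = 6 to 0.129 × 158 = 20.
- Children misclassified = children with mixed scores × share with at least one moderate sign and no severe item. The documents do not give that share. If it were 10% to 30%, the count would be 6 × 0.10 = 0.6 to 20 × 0.30 = 6, roughly 1 to 6 children over the three arms.

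**The case against.** The strongest reply is that the consequence is small. Section 3.1 lists thalamic NAA as the Phase 2 primary outcome and quantifiability of NAA as the secondary. Death or disability is in neither list. Section 7 specifies a t-test on NAA and a sample size built on an NAA difference of 0.5 and SD of 0.8, with no analysis of disability. Only the study summary ties the NAA outcome to predicting adverse neurodevelopment. This stands: the trial's primary result and power do not depend on the definition. The planned categorisation of scores may also keep low scores visible, but it does not repair the composite.

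A reader might infer more than the text supports:

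- **That 6–20 adverse outcomes will be missed.** That range counts every child with mixed scores. Those with no moderate sign are not adverse even under the corrected wording, and those with GMFCS 3–5, hearing aids or blindness are already severe.
- **That children with composites of 55 and 86, or with GMFCS 2, seizures and scores of 90, show the same fault.** They do not. No milder child is classed as worse, so these are strict thresholds, and the fix leaves them unchanged. The same goes for the general demand that both composites be below 70, and for preferring an any-one-of rule for moderate disability.
- **That the outcome cannot be compared with the 48% rate of death or moderate/severe disability in section 1.1.** The protocol does not say how disability was defined for that figure.
- **That allowing BSID-IV while giving BSID-III cut-offs belongs to this defect.** It is a separate matter of detail that an analysis plan may settle.

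**Conclusion.** The gap is real and follows from the wording of section 6.1 alone. It is confined to survivors with one composite below 70, the other 70–84, at least one moderate sign and no other severe item. Each such child is counted as not adverse while a milder child is counted as adverse, so the direction of the error is certain: the adverse-outcome count can only be too low.

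The size is not known. The 6–20 of 158 is a ceiling conditional on the assumed score distributions and 28% mortality. The 1 to 6 rests on a further assumed share. Harm is limited to the 18 to 24 month adverse outcome and whatever uses it. The point merits correction because the rule is wrong as written and cheap to repair, not because it threatens the main result.

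**What to change.** Replace the moderate definition in section 6.1 with: not severe, both cognitive and language composites below 85, and one or more of "GMFCS level 2, hearing impairment with no need for amplification or a persistent seizure disorder".

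This makes the moderate category adjoin the severe one, removes every inversion and reclassifies no child downward. It costs one sentence and should be made before follow-up data are analysed, since a later change could look driven by the results. No extra data are needed, because the same assessments supply every item. The adverse-outcome rate may be slightly higher than under the present wording.

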6.2. Incidental Findings

If an incidental finding is observed during a procedure which is carried out as part of the research, and it is considered a significant abnormality then the study team should report these to the PI who should take action accordingly.

Incidental finding will be feedback to the participants and to the clinical care team or participants GP in writing.

7. STATISTICS AND DATA ANALYSIS

We expect to recruit at least 60% of the eligible population and to have adequate quality data on the primary outcome for the main trial (i.e. thalamic N-acetylaspartate concentration) in >95% of the recruited babies.

We will use an unpaired t-test to estimate the difference in thalamic/basal ganglia NAA concentration between infants receiving erythropoietin and Darbepoetin alfa.

The standard deviation of [NAA] in the MARBLE study was 0.8. To detect a difference of 0.5 mmol/kg wet weight of [NAA] at 90% power and 0.017 significance, 71 infants will be required for each of the 3 groups for unadjusted analysis. The total sample size is increased to 220 to account for neonatal mortality and any unusable data due to motion artefacts. Data and all appropriate documentation will be stored for a minimum of 10 years after the completion of the study, including the follow-up period.

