3.1 STUDY OUTCOME MEASURES	10
4. PARTICIPANT ENTRY	11
4.1 INCLUSION CRITERIA	11
4.2 EXCLUSION CRITERIA	11
4.3 WITHDRAWAL CRITERIA	11
5. ADVERSE EVENTS	11
5.1 DEFINITIONS	11
5.3 REPORTING PROCEDURES	12
6. ASSESSMENT AND FOLLOW-UP	13
7. STATISTICS AND DATA ANALYSIS	13
8. REGULATORY ISSUES	13
8.1 ETHICS APPROVAL	13
8.2 CONSENT	14
8.3 CONFIDENTIALITY	14
8.4 INDEMNITY	14
8.5 SPONSOR	14
8.6 FUNDING	14
8.7 AUDITS	14
9. STUDY MANAGEMENT	15
10. PUBLICATION POLICY	15
11. REFERENCES	15
12. APPENDICES	17

GLOSSARY OF ABBREVIATIONS

EPO	Erythropoietin
DARBE	Darbepoetin alfa
NAA	N-acetylaspartate
MR	Magnetic resonance
HIE	Hypoxic Ischemic Encephalopathy
NE	Neonatal encephalopathy
MRS	Magnetic resonance spectroscopy
LAC	Lactate
U	Units
KG	Kilograms
LMIC	Low and middle-income countries
µG	Micrograms
IV	Intravenous
SNR	Signal to Noise Ratios
EEG	Electroencephalography

STUDY SUMMARY

TITLE Erythropoietin and Darbepoetin in Neonatal Encephalopathy (EDEN) study

DESIGN 3 arm open label pilot randomised controlled trial.

AIMS To examine the physiological effects of erythropoietin (Epo) and Darbepoetin alfa (Darbe) therapy on proton magnetic resonance spectroscopy thalamic N-acetylaspartate (NAA) level in babies with neonatal encephalopathy undergoing cooling therapy.

OUTCOME MEASURES

Phase 1

Primary outcome

Optimization of the signal to noise ratios (SNR) for MR spectroscopy at 1.5Tesla and 3Tesla, using clinical acceptable scan duration at 1.5 Tesla.

Phase 2

Primary outcome

Mean (SD) of thalamic NAA level in babies treated with Epo and Darbe when compared with untreated infants for predicting adverse neurodevelopment.

Secondary outcome

Number of babies in whom thalamic NAA level could be accurately quantified in 3Telsa and 1.5Tesla MR scanners.

POPULATION 20 Adult Healthy Volunteers
220 newborns with hypoxic ischemic encephalopathy.

ELIGIBILITY

Phase 1: Adults

Inclusion Criteria

1. >18 years old.

Exclusion Criteria

1. Adults with disease.
2. Adults with metal implant fitted, such as a pacemaker or artificial joint
3. Pregnancy.

Phase 2: Infants

Inclusion Criteria

1. Age \leq 24 hours
2. Birth-weight $>$ 1.8 kg
3. Gestation \geq 36 weeks
4. Need for continued resuscitation at 10 minutes after birth and/or 10 minutes Apgar score $<$ 6

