An EPO-induced high haematocrit can also cause brain injury²². However, babies with NE usually have lower haematocrits from perinatal events or from frequent blood sampling for clinical monitoring²²⁻²³. Zhu et al²³ compared two groups of term infants affected with NE: 83 received erythropoietin and 84 received conventional treatment. Haemoglobin and reticulocyte levels decreased significantly at 2 weeks after birth in the control group, but this decrease was prevented in the erythropoietin group.

Basegra et al²⁴, in the DANCE study reported that none of the most common complication of prolonged darbe treatment were found in the darbe- treated term infants. And more recently, Juul et al²⁵ randomised 741 preterm infants to high dose erythropoietin versus placebo and found no meaningful differences between groups in any serious adverse events, including those known to occur in adults who receive long-term erythropoietin treatments.

Benefits of the study

The data from this study will provide key feasibility information for future neuroprotection trials. Firstly, the study will inform if multicentric trials using thalamic NAA can be conducted in a setting with both 1.5 Tesla and 3 Tesla MR scanners.

Secondly, this study will provide a Go/No Go signal for a subsequent phase II placebo controlled randomised controlled trial to examine the clinical benefits of Epo on neurodevelopmental outcomes in cooled infants with neonatal encephalopathy.

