3. STUDY DESIGN

This study will be conducted in two phases:

Phase 1: This phase will be conducted at Imperial NHS trust and Imperial College London, recruiting 20 healthy adult volunteers over a 2-month period. All volunteers will be scanned at 1.5 Tesla and 3Tesla MR scanners, and the sequences will be optimised to obtained comparable thalamic NAA levels.

Phase 2: This phase will be conducted in 15 tertiary neonatal units in the UK over a 2-year period; 7 with 3Tesla MR scanners and 8 with 1.5 Tesla MR scanner, using the optimised MR spectroscopy sequences.

Babies (>36 week gestation and birthweight >1.8kg) requiring resuscitation at birth will be screened for eligibility, and recruited if there is evidence of acute perinatal asphyxia (metabolic acidosis in cord and/or blood gas (pH<7.15; BE >-12) within 1h of birth; acute obstetric event) AND the need for continued resuscitation or ventilation at 10 minutes and a 10 min Apgar score <6

AND evidence of moderate or severe HIE on an NICHD neurological examination performed between 1 and 6h of birth AND cooling was initiated before 6 h of age. Babies with mild HIE, and those cooled after 6 hours or with life threatening congenital malformations will be excluded.

After informed parental consent, a total of 220 babies with HIE (aged <24 hours) undergoing therapeutic hypothermia will be randomised to one of the following groups

- Arm 1: Erythropoietin (1000 U/kg) IV once a day x 5 doses along with cooling therapy
- Arm 2: Darbepoetin Alpha (10 mcg/kg) IV single dose given less than 24 hours of age along with cooling therapy.
- Arm 3: Cooling only (usual care)

Electroencephalography (EEG)

Babies recruited from Imperial NHS trust will have a 16-channel video electroencephalography (EEG), and those recruited from other centres will have amplitude integrated EEG (aEEG) measurements for the first 80 hours. The video EEG will be acquired and uploaded into a cloud based sever. This system allows a variety of research EEG double reporting options. Neonatal seizures will be classified based on their diagnostic certainty into 5 levels, as defined by the Brighton Collaboration (<https://www.brightoncollaboration.org/peer-review/GAIA-Neonatal-Seizures.html>).

Blood samples

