3.1 STUDY OUTCOME MEASURES

Phase 1:

Primary Outcome Measures

- Similar signal to noise ratios (SNR) for MR spectroscopy at 1.5Tesla and 3Tesla, using clinical acceptable scan duration at 1.5 Tesla.

Phase 2:

Primary outcome measures

- Mean (SD) of thalamic NAA level in babies treated with Epo and Darbe when compared with untreated infants.

Secondary outcome measures

- Number of babies in whom thalamic NAA level could be accurately quantified in 3Telsa and 1.5Tesla MR scanners.

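### The one test stated for the primary outcome compares Epo with Darbe and omits the comparisons with cooling alone that the primary outcome, and the sample size in the same section, call for

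*Protocol*

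**What the plan says.** The Phase 2 primary outcome in Protocol section 3.1 is "Mean (SD) of thalamic NAA level in babies treated with Epo and Darbe when compared with untreated infants". The Study Summary gives the same contrast and adds a phrase about predicting adverse neurodevelopment. The Study Design section randomises babies to Epo with cooling, Darbe with cooling, or cooling only.

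Section 7 then gives the only test of NAA in the document: "We will use an unpaired t-test to estimate the difference in thalamic/basal ganglia NAA concentration between infants receiving erythropoietin and Darbepoetin alfa".

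The next paragraph of section 7 sizes the trial. It takes an SD of 0.8 from a previous cohort, a target difference of 0.5 mmol/kg, 90% power and a level of 0.017, and concludes that "71 infants will be required for each of the 3 groups for unadjusted analysis". Deaths and unusable scans are then allowed for by raising the total to 220.

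The Background (Benefits of the study) says that "this study will provide a Go/No Go signal for a subsequent phase II placebo controlled randomised controlled trial", and describes that later trial as one of Epo in cooled infants.

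**The concern.** The primary outcome asks whether each drug changes NAA relative to babies who are cooled without it. The stated test asks whether the two drugs differ from each other. These are different questions, and the second does not answer the first: two drugs that work equally well and two that do nothing both have a true Epo–Darbe difference of zero.

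This is not a detail that a statistical analysis plan would be expected to supply. The protocol does state a comparison, and it conflicts with the protocol's own primary outcome. A later plan that follows section 7 abandons section 3.1, and one that follows section 3.1 departs from section 7. The trial is open label, so an unresolved primary contrast also leaves room to settle it after results by arm are known.

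The same sentence widens the measured region to thalamic/basal ganglia. The outcome definitions, the opening paragraph of section 7 and the single thalamic voxel described under MR Imaging and spectroscopy all say thalamic.

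**Working it through.** **Inputs (all from Protocol section 7).** Difference δ = 0.5 mmol/kg wet weight; SD σ = 0.8; power 90%; significance level 0.017; 71 per group in 3 groups. Sidedness is not stated; two-sided is assumed and is checked in step 1.

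**1. Reproduce the plan's figure.**

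Normal approximation: n = 2[σ(z₁₋α/₂ + z₁₋β)/δ]² = 2[0.8 × (2.387 + 1.282)/0.5]² = 68.9, so 69 per group.

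Exact two-sided unpaired t-test at n = 71:
- standard error = 0.8 × √(2/71) = 0.1343
- noncentrality = 0.5/0.1343 = 3.724
- degrees of freedom = 2 × 71 − 2 = 140
- critical value at two-sided 0.017 = 2.416
- power = 90.3%

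At n = 70 the power is 89.8%, so 71 is the smallest number that reaches 90%. The plan's figure reproduces exactly. A one-sided 0.017 gives 60 by the normal approximation and does not reproduce it, so two-sided is the reading that fits.

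**2. What the level and the group count imply.** 0.05/3 = 0.0167, which rounds to 0.017. Three groups give three pairwise comparisons: Epo–control, Darbe–control and Epo–Darbe. A level of 0.05/3 with three groups of 71 matches that family. The single test as written, at two-sided 0.05, would need 55 per group by the exact t-test (54 by the normal approximation) and no third arm. The sample size therefore fits three comparisons, while the test sentence names one.

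**3. What the stated test would show.** Write each arm's mean NAA as the control mean plus that drug's effect. The stated test then targets (Epo effect − Darbe effect).

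| True effects against cooling only | Epo–Darbe difference | Probability that the stated test rejects |
|---|---|---|
| Both 0 | 0 | 1.7% |
| Both +0.5 mmol/kg | 0.5 − 0.5 = 0 | 1.7% |

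In the second row each comparison with control, had it been stated, would have 90.3% power.

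**4. After the correction.** Each of the three pairwise comparisons at two-sided 0.017 needs 71 per group and has 90.3% power. The total for analysis stays at 3 × 71 = 213, within the planned 220. If only the two comparisons with control were primary, at 0.05/2 = 0.025 each, 65 per group would reach 90%, and 71 per group gives 92.6%.

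**The case against.** The best reply is that comparisons with control were plainly intended. Section 7 sizes three groups at a third of 0.05, and no family of three pairwise comparisons among three arms can leave the control arm out. On this view the test sentence merely dropped a few words. Most of that stands. It rules out two stronger readings that a reader might infer: that section 7 makes no use of the cooling-only arm, and that 0.017 is itself a mistake. The control arm is in the sample size, and 0.017 is the clearest sign of the intended family. Even if only two control comparisons were meant, testing them at 0.017 would be conservative, not wrong. What the reply does not do is remove the contradiction: no sentence names those comparisons or links 0.017 to them.

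A second reply is that this is a pilot, that its objective is to describe means and standard deviations, and that the Background ties Go/No Go to no particular test. This too has force. The documents do not support saying that the trial cannot deliver such a signal, since it will collect control data and has the power to use them. The narrower statement holds: the one test written down cannot inform that decision for Epo against usual care.

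A reader might also take the word *receiving* as a plan to analyse babies as treated. One participle does not establish that. The Study Design section says that babies are randomised to groups, and the analysis population is commonly left to the statistical analysis plan.

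**Conclusion.** The test sentence in section 7 is wrong as written. It contradicts the primary outcome in section 3.1 and the Study Summary, and it does not match the sample size in its own section. Taken literally, it rejects with probability 1.7% both when the two drugs are equally effective and when neither works. The 1.7% assumes that the two true effects are equal and that the test is run at the plan's 0.017.

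The fault lies in the stated analysis and not in the design. With 71 analysable babies per group, SD 0.8, a difference of 0.5 mmol/kg and a two-sided test, each comparison with cooling only has 90.3% power. The correction matters because it concerns the primary comparison. The change of region to thalamic/basal ganglia is a lesser inconsistency in the same sentence.

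**What to change.** Replace the test sentence in section 7 with wording to this effect:

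> The primary comparisons are Epo plus cooling versus cooling only, and Darbe plus cooling versus cooling only, on thalamic NAA, with babies analysed by randomised group using unpaired t-tests. Epo versus Darbe [is / is not] the third primary comparison. Each primary comparison is tested at a two-sided level of 0.017 (0.05/3).

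The sponsor should complete the bracketed choice; with all three comparisons primary, 0.017 matches the family exactly. Use *thalamic* in place of *thalamic/basal ganglia*, to agree with the single thalamic voxel in the imaging section.

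Restricting the primary family to the two comparisons with control at 0.025 each (92.6% power at 71 per group) is an option, but correcting the error does not require it.

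The cost is a protocol wording change. It needs no extra babies, scans or data, and the sample size stays at 71 per group and 220 in total.

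### Section 7 plans an unadjusted t-test on NAA although the NICHD encephalopathy grade is known before randomisation; the cost is some precision, not bias

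*Protocol*

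**What the plan says.** Section 7 gives the method and the size of the NAA comparison.

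- Method: "We will use an unpaired t-test to estimate the difference in thalamic/basal ganglia NAA concentration between infants receiving erythropoietin and Darbepoetin alfa". No covariate is named.
- Inputs: "The standard deviation of [NAA] in the MARBLE study was 0.8", and "To detect a difference of 0.5 mmol/kg wet weight of [NAA] at 90% power and 0.017 significance".
- Result: "71 infants will be required for each of the 3 groups for unadjusted analysis".

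Study Design requires "evidence of moderate or severe HIE on an NICHD neurological examination performed between 1 and 6h of birth" before a baby is recruited. Section 8.2.2 places randomisation after parental consent. The examination that shows the grade therefore precedes allocation.

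No section names stratification by grade, or a model that contains it. Section 3.1 defines the primary outcome as NAA in treated babies compared with untreated babies. The Introduction, under Benefits of the study, says the trial will give a Go/No Go signal for a later trial of Epo.

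**The concern.** NAA was chosen as the outcome because it reflects brain injury. The scan is done at 1 to 2 weeks and no pre-treatment NAA is planned, so clinical severity at entry is a natural baseline covariate. If grade is related to NAA, the variation it explains stays in the error term of a t-test, and the intervals are wider than the collected data allow. The protocol does name a method, so the point concerns a stated choice and not detail left for a later document. At stake is the precision of the arm differences, in a study meant to inform whether a further trial goes ahead.

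**Working it through.** **Inputs from section 7.** SD 0.8, difference 0.5 mmol/kg, significance level 0.017 (about 0.05/3), power 90%, 71 per arm. Sidedness is not stated; two-sided reproduces the figure.

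**Input that the documents do not give.** The correlation rho between NICHD grade and NAA. The background section reports that NAA predicts 2-year outcome with an AUC of 0.99, but that is not a relation between entry grade and NAA. I assume rho from 0 to 0.5.

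**Step 1: the plan's own figure.** The exact two-sample t calculation (noncentral t, two-sided 0.017) gives 71 per arm. The normal approximation gives 69. One-sided would give 61 (exact), which does not match.

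Unadjusted SE of a difference = 0.8 × √(2/71) = 0.134 mmol/kg. Noncentrality = 0.5/0.134 = 3.72. Power = 90.3%. The plan's 71 is correct.

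**Step 2: adjusting for grade.** Residual SD = 0.8 × √(1 − rho²); SE = residual SD × √(2/71); one degree of freedom is spent on a two-level grade.

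| Assumed rho | Residual SD | SE | Power at 71 per arm | n per arm for 90% |
|---|---|---|---|---|
| 0 | 0.800 | 0.134 | 90.3% | 71 |
| 0.2 | 0.784 | 0.132 | 91.5% | 68 |
| 0.3 | 0.763 | 0.128 | 93.0% | 65 |
| 0.4 | 0.733 | 0.123 | 94.9% | 60 |
| 0.5 | 0.693 | 0.116 | 96.9% | 54 |

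Spending two degrees of freedom (three levels) changes none of these figures at the precision shown.

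**Step 3: where chance imbalance belongs.** The part of the unadjusted difference due to chance imbalance in grade has SD rho × 0.8 × √(2/71), which is 0.067 mmol/kg at rho 0.5. The remaining part has SD 0.116. Then 0.067² + 0.116² = 0.0045 + 0.0135 = 0.0180 = 0.134². The imbalance is one component of the unadjusted SE, and the planned interval and test already allow for it.

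**Step 4: what the assumed correlations imply.** For a two-level grade with a share p severe, the gap in mean NAA between severe and moderate babies is rho × 0.8/√(p(1 − p)). With p assumed between 20% and 40%, rho 0.2 means a gap of about 0.33 to 0.40 mmol/kg, rho 0.3 about 0.49 to 0.60, rho 0.4 about 0.65 to 0.80, and rho 0.5 about 0.82 to 1.00.

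**The case against.** The case against raising this has real weight.

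- **Nothing is miscalculated.** A t-test is valid and unbiased under randomisation, and 71 per arm reaches the target without help. That stands: the point is about efficiency only.
- **Sizing without covariates does not forbid adjusting later.** True, and it is common and conservative. But section 7 also names the test, and that test has no covariates. A statistical analysis plan that is not shown may already adjust.
- **The t-test sentence compares Epo with Darbe.** It does not describe the primary comparison with untreated babies, or the Epo comparison relevant to the Go/No Go signal. That stands, and it is a more serious fault of the same section. That the comparisons with control are also unadjusted can be read only from the sample-size sentence, which covers all three groups.
- **The gain is assumed.** It stays below 5 percentage points at 71 per arm unless rho exceeds about 0.4, and correlations of 0.4 to 0.5 imply severity gaps larger than the 0.5 mmol/kg drug effect being sought (step 4).
- **The covariate is not settled.** Study Design excludes mild encephalopathy; section 4.1 admits it and does not mention the NICHD examination.

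A reader might also infer that chance imbalance in severity biases the Go/No Go estimate, over and above the loss of power. The documents do not support that. Over randomisation the imbalance is variance already counted in the 0.134 mmol/kg, and no numerical Go/No Go rule is given from which to trace an effect.

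**Conclusion.** The concern holds as a loss of precision. The protocol plans an unadjusted comparison although a severity grade is known before allocation, and gives it no role in the analysis. Against 90.3% unadjusted, power at 71 per arm would rise by 1.2 points at rho 0.2, 2.7 at 0.3, 4.6 at 0.4 and 6.6 at 0.5. If grade and NAA are unrelated, power stays at about 90.3%. These figures rest on the plan's SD and difference, a two-sided test, 71 evaluable babies per arm, and a correlation that is wholly assumed.

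It would be too strong to read this as an invalid test, an underpowered trial or a biased estimate; the checks above rule out all three. It is an inexpensive improvement whose benefit is uncertain in size and whose downside is negligible.

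**What to change.** 1. Reconcile Study Design and section 4.1 on mild encephalopathy. This decides whether the grade has two or three levels, and so one or two degrees of freedom.
2. In section 7, make the primary analysis a linear model of NAA on randomised arm and the NICHD grade recorded at 1 to 6 hours. Report each active arm's difference from cooling only, in line with the primary outcome in section 3.1, with a confidence interval at the 0.017 level (98.3%). The same rewrite corrects the Epo-versus-Darbe wording.
3. Keep the unadjusted t-test as a sensitivity analysis.
4. Keep 71 per arm and describe it as conservative for the adjusted analysis.

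The cost is a sentence or two in section 7, carried into the statistical analysis plan. It needs no extra babies or visits, and no data beyond an examination already required at entry.
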